Potentially eligible subjects will be asked to complete the Informed Consent process, at which point the subjects will read through the IRB-approved consent form, and will meet with a research staff member who will answer any questions, explain the schedule of study procedures, and review the risks and benefits of the study. Subjects will be informed about the experimental nature, purpose, risks, and benefits of the study in accordance with procedures of the Partners IRB. There will be no time-limit placed on the consenting process. Research staff members understand that the consent is a process and not simply a matter of signing and dating the consent form. Either the PI or one of the Co-Investigators (serving as designees of the PI) will be available to help explain the study and answer questions. Once the subject consents to participate in the study, the subject will sign and date the consent form along with a member of the research staff. The subject will be provided with a copy of the consent form and the original will be stored in a secure location by a member of the study staff.

Participants will be randomly assigned to receive either ICBT or IDC. This randomization will be stratified by the following variables: (1) presence of a medication for anxiety, (2) gender, (3) type of opioid medication (agonist/partial agonist vs. antagonist), and (4) severity (defined by presence vs. absence of opioid use since initiating pharmacotherapy for opioid use).

V. STUDY PROCEDURES

All participants will receive 12 individual weekly sessions of ICBT or IDC and will complete assessments at baseline, week 12, and 1- and 3-month post-treatment follow-up visits. Breath alcohol screens will be conducted at each session and assessment visit to confirm absence of acute alcohol use. Procedures for response to a positive breathalyzer screen are specified below in Section VII. Qualitative exit interviews will be conducted at the completion of treatment. These interviews will focus on issues related to feasibility and acceptability, such as identifying the most and least helpful sessions and areas for improvement. Details of the procedures are included below.

V.1. Eligibility and Baseline Assessment

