The stress reactivity paradigm includes two imagery conditions (neutral-relaxing, stress related) and a laboratory session. This paradigm will be completed at pre- and post-treatment assessments. During a visit prior to laboratory sessions, participants will complete two Scene Development Questionnaires (Sinha & Tuit, 2012) that are designed to collect information about each imagery condition (a non-drug-related stressful event in their life, and a neutral-relaxing event); scripts for the imagery conditions will be developed using the information collected. Each script will be written, recorded, and edited by trained research staff in order to ensure that scripts are standardized in terms of length and content. During laboratory sessions, participants will listen to each script. The order of the scripts will be randomized. Psychophysiological measures (skin conductance) will be collected before, during, and after each imagery script. Skin conductance response will be collected using a Biopac MP150 system running AcqKnowledge 4.4 software (Biopac Systems Inc., USA) and the Biopac electrodermal activity amplifier (EDA100c). Skin conductance response is used as an index of physiological arousal, and therefore stress reactivity. Subjective measures that will be administered prior to and following each imagery condition include the Positive and Negative Affect Scale (Watson, Clark, & Tellegen, 1988), and the Opioid Craving Scale (Weiss et al., 2003) that has been adapted to assess craving in the present moment (i.e., “right now”). Following each imagery script participants will also be asked to rate how “clearly and vividly” they were able to imagine the scenario on a 10-point visual analog scale.

V.4.4. Urine Toxicology

Participants will provide weekly urine samples to screen for drug use. Although opioid use is the primary outcome for this trial, the presence of other substances of abuse will be used as secondary outcome. We will use the Alere Toxicology iCup 13 panel drug test screening cup, which tests for the presence of the following substances: cocaine, marijuana, opiates, amphetamines, methamphetamines, phencyclidines, benzodiazepines, barbiturates, methadone, tricyclic antidepressants, oxycodone, propoxyphene, and buprenorphine. We will also use a Drug Screen Test Dip Card to test for fentanyl in the urine sample.

V.4.5. Measurement of Sex Hormones and Menstrual Cycle Phase

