Female participants will provide saliva samples and will report descriptive data on menstrual cycle phase in order to measure fluctuations in estradiol and progesterone throughout the study period. Salivary assays of estradiol and progesterone will be performed in duplicate and in

accordance with manufacturer specifications at the Laboratory for Biological Health Psychology at Brandeis University. Saliva samples will be collected using the passive drool method and according to recommended collection procedures. Samples will be collected at baseline (immediately prior to the Escape Go/NoGo Task) and at each weekly session. In addition to measurement of salivary estradiol and progesterone, we will also collect descriptive data on menstrual cycle phase (with the Menstrual Cycle Information form), following recommendations for optimizing measurement of menstrual phase (Allen et al., 2016). Specifically, we will utilize both self-reported onset of menses and weekly hormone data to characterize menstrual cycle phase throughout the trial. We will also assess for presence, type, dose, and compliance with birth control at each time point. Furthermore, using the interviewer-administered Saliva Sample Activity Documentation form, we will collect information on participant activity in the past 12 hours that may affect saliva collection.

VI. BIOSTATISTICAL ANALYSIS

Data from this randomized controlled trial will be analyzed using descriptive and qualitative analytic methods as well as traditional significance tests. Measures of patient satisfaction will be considered along with qualitative exit interviews to determine the acceptability of the treatment. Randomized groups will be compared with respect to baseline demographic and clinical variables using t-tests and chi-square tests; if significant group differences are identified in any variables known to be highly predictive of outcome, these variables will be adjusted for via their inclusion as covariates. These covariates will also be summarized with descriptive statistics and graphical methods to determine the most appropriate way to incorporate them in the analyses (e.g., continuous or categorical representation). All outcome analyses will utilize an intent-to-treat approach, complemented by exploratory completer analyses.

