The hypothesis that I-CBT will yield greater reduction in opioid use and anxiety symptoms will be tested using separate linear mixed effects models for opioid use (weeks of use in the previous 4 weeks) and anxiety (HARS score) examining the main effect of treatment condition and its interaction with time on each outcome. The correlation among the repeated measures of the dependent variable will be appropriately accounted for via the inclusion of random subject effects (e.g., random intercepts and slopes for time). Covariates will include pre-treatment values of the dependent variable and any baseline demographic or clinical variables identified as necessary covariates in preliminary analyses.

To test the hypothesis that baseline stress reactivity is associated with treatment outcome at post-treatment (week 12), linear regressions will be utilized with primary opioid and anxiety outcomes at week 12 as the dependent variables and post-stress task anxiety, craving, and heart rate variability as independent variables, co-varying for baseline severity and any other covariates identified in preliminary analyses. In addition, to test the hypothesis that reduction in stress reactivity over time will be greater in the I-CBT condition, a linear mixed effects model will be conducted examining whether stress reactivity decreased from pre- to post-treatment and whether groups differed with respect to this change; this analysis will include the main effects of time and group and the time x group interaction. The correlation among repeated measures of the dependent variable will be accounted for via the inclusion of random subject effects.

With repeated assessments over 7 months of study participation, some amount of missing data is inevitable. Extensive efforts will be made throughout all stages of follow-up to minimize missing data by vigorous outreach, including to any participants who elect to dropout of treatment prior to completion. For all of the proposed analyses, we will use statistical methods (e.g., linear

mixed effects models) that incorporate partially observed data on participants who are lost to follow-up.

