We do not expect more than a 10% loss to follow-up (see C.4); nonetheless, the sample size of 54 participants was selected to provide adequate degrees of freedom to estimate the treatment effect size and its reliability, even when allowing for up to 20% loss to follow-up. In this Stage 1 trial, we will focus on the estimation of effect sizes and clinically-significant change (as defined by Jacobson & Truax, 1991). If promising results (i.e., presence of clinically-significant change) are detected, these data will provide an estimate of the reliability of the effect to inform power calculations for a larger Stage 2 clinical trial. Although the focus of this trial is the estimate of an effect size and its reliability, we have conducted a power analysis for the proposed sample size; effect sizes are expressed as standardized differences in means for ease of interpretation. For Aim 2, based on unpublished data from previous clinical trials, we anticipate a small correlation between repeated measures of the opioid use outcome ($r < .20$) and a small to medium correlation ($r = 0.42$) for the HARS. Thus, the proposed sample size would provide adequate power (power of at least 0.80) to detect a minimum between-group difference from baseline to end of treatment in the magnitude of a large effect size ($d = .70-.75$). For Aim 3, based on previous studies examining stress reactivity and alcohol and cocaine use following treatment, which have consistently reported medium to large effect sizes (Sinha et al., 2009; 2011), the proposed sample size would provide adequate degrees of freedom to detect an effect size in the range of high medium to large.

VII. RISKS AND DISCOMFORTS

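### The Aim 3(b) stress-reactivity model makes no planned use of the baseline value, so it gives up precision that the trial's own data could supply (a loss of precision, not a bias)

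*Combined protocol and SAP*

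**What the plan says.** Specific Aim 3(b) in Section II hypothesises that stress reactivity falls more from baseline to post-treatment under ICBT than under IDC. Section V.4.3 fixes the measurement occasions: "This paradigm will be completed at pre- and post-treatment assessments". There are thus two visits.

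Section VI gives the terms of the mixed model: "this analysis will include the main effects of time and group and the time x group interaction". It adds: "The correlation among repeated measures of the dependent variable will be accounted for via the inclusion of random subject effects". No pre-treatment covariate and no common baseline mean is mentioned for this model.

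The neighbouring analyses in Section VI differ. For the Aim 2 models, "Covariates will include pre-treatment values of the dependent variable". The Aim 3(a) regressions adjust for baseline severity. The section's general rule, "these variables will be adjusted for via their inclusion as covariates", applies only when the arms differ significantly at baseline on a variable known to predict outcome strongly.

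For Aim 3 the power paragraph says only that the sample gives "adequate degrees of freedom to detect an effect size in the range of high medium to large". It states no numeric effect size, power or pre-post correlation for stress reactivity.

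**The concern.** Randomisation makes the arms equal in expectation before treatment. A model with a group main effect ignores this: it estimates a separate baseline mean for each arm and measures the treatment effect as the difference between two changes. The noise in the baseline measurement then enters the treatment estimate at full weight. If the pre-post correlation is modest, subtracting the whole baseline value adds more noise than it removes.

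Aim 3(b) is the trial's randomised comparison of a proposed mechanism, and Section VI says this Stage 1 trial is mainly meant to estimate effect sizes and their reliability. An avoidably wide interval works against that purpose. Participants also give time, and are paid extra under Section V.3, for the baseline session whose information is used inefficiently.

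**Working it through.** **Inputs.** Total sample 54 (Section VI). Section IV says "Participants will be randomly assigned to receive either ICBT or IDC" without giving a ratio, so 27 per arm is assumed. Two-sided 5% is assumed, because no significance level is stated. The correlations are r = .42 for the HARS and r below .20 for opioid use (Section VI, both for Aim 2). For stress reactivity r is not given, so .20, .42 and .60 are used as a range; nothing in the documents supports .60 in particular. Effects d are in outcome-SD units, with equal SDs at the two visits.

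**Step 1: the plan's own figure.** The only numeric power statement is for Aim 2: d = .70 to .75 at power of at least .80. With a normal approximation and baseline adjustment, detectable d = (1.96 + 0.84) × √(2/27) × √(1 − r²) = 0.762 × √(1 − r²).
- r = .42: 0.762 × 0.908 = 0.69
- r = .20: 0.762 × 0.980 = 0.75

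This reproduces the plan's figure with all 54 analysed. For a change score the multiplier is √(2(1 − r)), which gives 0.82 (r = .42) and 0.96 (r = .20) and does not reproduce it. The Aim 2 sizing is thus consistent with the adjustment that Aim 3(b) leaves out.

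**Step 2: what the Aim 3(b) test is.** With two visits, one score per visit and complete data, the time-by-group coefficient is the difference in mean change. A random-intercept model fitted to simulated data (27 per arm) gave an interaction of −0.7264 with t = −2.8146. The two-sample t-test on change scores gave the same two numbers.

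**Step 3: the variance ratio.** Planned over adjusted = 2(1 − r)/(1 − r²) = 2/(1 + r).
- r = .20: 2/1.20 = 1.67 (67% penalty)
- r = .42: 2/1.42 = 1.41 (41%)
- r = .60: 2/1.60 = 1.25 (25%)

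The confidence interval is wider by the square root of the ratio: about 29%, 19% and 12%. Simulation at 54 participants gave ratios of 1.64, 1.39 and 1.23, slightly lower because ANCOVA must also estimate a slope.

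**Step 4: power and detectable effect (noncentral t, 27 per arm, complete data).**

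| r | Power at d = .70, planned vs adjusted | Detectable d at 80% power, planned vs adjusted |
|---|---|---|
| .20 | 51% vs 73% | .98 vs .76 |
| .42 | 65% vs 79% | .84 vs .70 |
| .60 | 81% vs 88% | .70 vs .62 |

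A comparison of post-treatment values alone detects d = .78. The change score does worse than this whenever 2(1 − r) exceeds 1, that is, whenever r is below .5.

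**Step 5: missing post-treatment values.** If a share m is missing at random and participants with only a baseline session stay in the mixed model, the ratio becomes 1 + (1 − m)(1 − r)/(1 + r). At the 20% loss that Section VI allows for:
- r = .20: 1 + 0.8 × 0.80/1.20 = 1.53
- r = .42: 1 + 0.8 × 0.58/1.42 = 1.33
- r = .60: 1 + 0.8 × 0.40/1.60 = 1.20

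At r = .42 the detectable d is then about .91 planned against .79 adjusted.

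**The case against.** **The planned test is valid and answers the stated question.** Aim 3(b) is worded as a difference in reduction, and the planned interaction estimates exactly that, with no bias and no inflation of type I error. This stands. The point is about efficiency only.

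**A reader might infer that the model fails to deliver the effect range claimed for Aim 3.** The documents do not support that. The sentence is verbal, gives no upper limit to a large effect, and rests on earlier studies of reactivity and later substance use. Those bear on the predictive question in Aim 3(a), not on the comparison of arms over time. No stated Aim 3 figure is contradicted.

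**The size is assumed.** No r for reactivity is given, and the Aim 2 correlations belong to other measures. This stands, and it is why a range is shown. The penalty shrinks as r rises (at r = .80 it is 2/1.80 = 1.11), but it stays above zero for any r below 1.

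**One score per visit is a simplification.** Section V.4.3 takes skin conductance before, during and after each of two scripts, with affect and craving ratings before and after each. Section VI does not say how these become one reactivity value. If within-session readings enter the model directly, the ratios above need not apply.

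**The general covariate rule might supply the adjustment.** It could do so by chance, after a significant baseline difference. That is not planned adjustment for precision.

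**The remedy has conditions.** A common baseline mean is justified if the baseline session precedes randomisation. Section IV does not give the timing, and Section V.4.3 requires an earlier visit to develop the scripts. ANCOVA would drop participants with only a baseline session, which sits badly with the commitment in Section VI to use partially observed data.

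**Stress reactivity is not a primary outcome.** Table 1 lists it under psychophysiological measures. This limits the importance of the point but not its correctness.

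**Conclusion.** The point holds as a free improvement in precision. As specified, the Aim 3(b) model leaves the baseline group difference free and plans no adjustment for pre-treatment reactivity. With one score per visit and complete data this costs 25% to 67% in variance for r from .60 to .20. With 20% of post-treatment values missing and baseline-only participants retained, the cost is about 20% to 53%. At the two correlations borrowed from Aim 2 (.42, and .20 as the upper bound for opioid use), the planned test would be less precise than ignoring the baseline session altogether.

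The algebra is certain; the size is not, because it depends on a correlation that the documents do not give, on equal allocation and on a two-sided 5% level. It would be wrong to read this as an invalid test or as a missed power claim.

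**What to change.** In the Aim 3(b) sentence of Section VI, keep pre- and post-treatment reactivity as outcomes, with time and time-by-group terms but no group main effect, so that both arms share one baseline mean. This still tests whether reactivity fell and whether the arms differ in that change, and it keeps participants who have only a baseline session.

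State in the same place that the baseline stress session takes place before randomisation, or at least before treatment starts, since the common baseline mean depends on it. Also name the single reactivity score that is analysed at each visit.

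ANCOVA of the post-treatment score on arm and pre-treatment score can serve as a fallback or sensitivity analysis, with the stated drawback that baseline-only participants drop out.

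The cost is a sentence or two of text. No new data are needed and the hypothesis is unchanged.

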Specific Aim 2. To examine the efficacy of ICBT for the improvement of opioid dependence and anxiety symptoms relative to Individual Drug Counseling (IDC). We hypothesize that patients will report greater pre-post reductions in interviewer-rated anxiety symptoms and less opioid use in ICBT relative to IDC.

Specific Aim 3. To examine the association between stress reactivity and treatment outcome in opioid-dependent patients. We hypothesize that: (a) higher levels of stress reactivity at baseline will be associated with more days of opioid use following treatment, and (b) reductions in stress reactivity from baseline to post-treatment will be greater in the ICBT group relative to the IDC group.

Specific Aim 4. To examine the association between ovarian sex hormones, negative reinforcement bias, and treatment outcome in opioid-dependent patients. We hypothesize that: (a) greater negative reinforcement bias will be associated with poor treatment outcomes, and that this association will be stronger in women than men, and (b) within women, high progesterone will be associated with lower negative reinforcement bias and less severe opioid symptoms (e.g., opioid craving, anxiety severity).

III. SUBJECT SELECTION

Participants will be recruited for a randomized controlled trial of the efficacy, feasibility, and acceptability of ICBT. We aim to enroll 54 participants in this trial, and anticipate that up to 110 participants will need to complete informed consent and screening in order to initiate treatment. Participants will be recruited via either: (1) invitation to participate by a member of the study staff, or (2) self-selection in response to posted advertisements.

III.1. Inclusion/Exclusion Criteria

Subjects will be **included** if they: (1) are age 18 or older, (2) meet *DSM-5* diagnostic criteria for opioid use disorder, (3) are currently receiving pharmacotherapy for opioid dependence (e.g., buprenorphine, buprenorphine-naloxone, naltrexone, Vivitrol), (4) have used opioids illicitly within the previous 90 days, (5) exhibit clinically-significant anxiety defined as a score of 14 or higher on a clinician-rated anxiety symptom severity scale (the Hamilton Anxiety Rating Scale), (6) meet *DSM-5* diagnostic criteria for a current diagnosis of an anxiety disorder, (7) are able to read and provide informed consent, and (8) intend to remain in the geographical area for the duration of the study period.

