Distress Intolerance Index. The Distress Intolerance Index (DII; McHugh & Otto, 2011) is a 10-item self-report measure of the intolerance of distressing states that was derived from a study of distress intolerance measures. The DII has demonstrated strong internal consistency reliability in clinical and unselected samples (McHugh & Otto, 2011) as well as strong concurrent and discriminant validity and distinguishes clinical from non-clinical groups (McHugh & Otto, 2012).

Drug Use Motives Questionnaire (DUMQ). The DUMQ (Mueser, Nishith, Tracy, DeGirolamo, & Molinaro, 1995) is a 15-item self report inventory designed to provide an assessment of coping, social and enhancement motives for alcohol use (Cooper, Russell, Skinner, & Windle, 1992). We will use a modified DMQ to assess non-alcohol drug use motives (as utilized by Mueser et al., 1995) with the addition of 5 items to assess for use of opioid for pain coping.

Exit Interview. Participants will be asked to complete an exit interview with a study investigator after the completion of the treatment. Participants will be given the opportunity to share feedback on their experience with the treatment and will be asked how well the treatment addressed their needs. This will be audiotaped and transcribed for analysis.

Fagerstrom Test for Nicotine Dependence (FTND). The FTND (Heatherton, Kozlowski, Frecker, & Fagerstrom, 1991) will be used as a continuous measure of nicotine dependence. The FTND has shown good internal consistency, a single dimension factor structure, and positive relationships with degree of nicotine intake as assessed by saliva cotinine. FTND items are combined with other smoking history items in this study.

Hamilton Anxiety Rating Scale (HARS). The HARS (Hamilton, 1959) is an interviewer-administered measure of anxiety symptoms. The Structured Interview Guide for the HARS (Shear et al., 2001) was developed to improve the reliability of the HARS and will be used in this study. This will be the primary outcome measure for the study.

Homework Compliance. Both participants and clinicians will separately rate compliance with homework/skills practice on a weekly basis with a form adapted from an assessment of homework compliance developed by Primakoff, Epstein, & Covi (1986).

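### The plan's label for results worth taking to Stage 2 makes no reference to IDC, so equal improvement in both arms would satisfy it

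*Combined protocol and SAP*

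**What the plan says.** Section VI describes the focus of the trial as follows: "In this Stage 1 trial, we will focus on the estimation of effect sizes and clinically-significant change", with the second term defined by a literature citation. The next sentence sets the label: "If promising results (i.e., presence of clinically-significant change) are detected, these data will provide an estimate of the reliability of the effect", the purpose being to plan the size of a Stage 2 trial. No other section defines promising results or gives another criterion for Stage 2.

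The rest of the plan is comparative:

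- **Aim 2 (Section II)** hypothesises "greater pre-post reductions in interviewer-rated anxiety symptoms and less opioid use in ICBT relative to IDC".
- **The Aim 2 models (Section VI)** are linear mixed models for opioid use and for HARS score, "examining the main effect of treatment condition and its interaction with time on each outcome".
- **The sample size (Section VI)** of 54 was chosen to give "adequate degrees of freedom to estimate the treatment effect size and its reliability", allowing for up to 20% loss to follow-up.
- **The power statement (Section VI)** refers to a "minimum between-group difference from baseline to end of treatment" of d = 0.70 to 0.75.

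**The concern.** The label and the question do not match. Clinically significant change is classified patient by patient, from that patient's own scores. Its presence can therefore be established within one arm, or in the pooled sample, without looking at the other arm. Aim 2 asks whether ICBT does better than IDC.

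Some improvement in both arms is plausible. Both arms receive 12 weekly individual sessions (Section V). Every patient is on pharmacotherapy for opioid dependence and enters with a HARS score of 14 or more (Section III.1). The documents do not allow the size of that shared improvement to be estimated.

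At stake is the meaning of one word in the trial's report. The results could be called promising, correctly under the plan, when the randomised comparison gives no sign that ICBT adds anything to IDC.

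**Working it through.** **1. The plan's own figure.** The power claim (at least 0.80 at d = 0.70 to 0.75) concerns the between-arm contrast. Alpha, sidedness, allocation ratio and formula are not stated; two-sided 0.05 and 1:1 are assumed here. With baseline adjustment, the outcome SD is multiplied by sqrt(1 − r²). At r = 0.42 (HARS), noncentral-t power is 0.794 at d = 0.70 with 27 per arm and 0.800 at d = 0.75 with 24 per arm. At r = 0.20 (upper end for opioid use), it is 0.788 at d = 0.75 with 27 per arm. The range is thus reached, or nearly so, under a standard method with little loss. Other variants give higher or lower figures. The present point does not depend on this calculation, which shows only that the trial was sized for a difference between arms.

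**2. What the label tests against what Aim 2 tests.** Let the proportion with clinically significant change be p in each arm, and the mean improvement m in each arm.

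| Quantity | Value under equal improvement |
|---|---|
| Clinically significant change present (the label) | Met whenever some patients change |
| Difference in proportions, ICBT − IDC | p − p = 0 |
| Difference in mean improvement, ICBT − IDC | m − m = 0 |

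This holds for any p above 0 and any m, so no assumed rate is needed. A stricter reading of presence, such as a minimum proportion of patients, raises the bar for p but leaves the last two rows at zero.

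**3. How precise a between-arm criterion would be.** Inputs from Section VI are N = 54, 20% loss (0.80 × 54 = 43.2, taken as 43, split 22 and 21) and r = 0.42 for the HARS. Assumed are 1:1 allocation and adjustment for the baseline value. In SD units:

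- SE = sqrt(1/n1 + 1/n2) × sqrt(1 − r²); half-width = t(0.975, N − 3) × SE.
- N = 54: SE = sqrt(2/27) × sqrt(1 − 0.1764) = 0.272 × 0.908 = 0.247; half-width = 2.008 × 0.247 = 0.496.
- N = 43: SE = sqrt(1/22 + 1/21) × 0.908 = 0.305 × 0.908 = 0.277; half-width = 2.021 × 0.277 = 0.560.
- Opioid use, r from 0.20 down to 0: half-width 0.535 to 0.546 at N = 54, and 0.604 to 0.617 at N = 43.

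**4. Why a responder comparison needs a missing-data rule.** With 20% loss, 0.20 × 27 = 5.4 patients per arm have no week 12 score. Counting all of them as changed in one arm and none in the other moves the difference by 5.4/27 = 20 percentage points, in either direction. The planned linear mixed models use partial data but do not classify such patients.

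**The case against.** The best defence is context. The sentence goes on to speak of the reliability of the effect, which echoes the treatment effect size and its reliability earlier in the same paragraph. If both arms improved equally, the effect passed to Stage 2 planning would be near zero and visibly unpromising, and nothing in the plan lets the label override it. This stands, and it is why the weight is small. It repairs the second half of the sentence, though, and not the condition in the first half. If a between-arm effect was meant, the definition should say so.

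A second objection is that the proposed wording sets no threshold, so a near-zero estimate with a wide interval could still be judged promising. That is true. In an estimation trial the label may remain a judgement; what changes is the quantity being judged.

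Three stronger readings are tempting, and the documents support none of them:

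- **The trial lacks an ICBT–IDC comparison.** Aim 2 and the mixed models supply it.
- **The label is a decision rule with a high false-positive rate.** The plan gives no decision rule and no rate of clinically significant change from which an error rate could be computed.
- **The label is also undermined by rival primary outcomes.** Section V.4.1 says of the HARS, "This will be the primary outcome measure for the study", and Section V.4.4 says "opioid use is the primary outcome for this trial". But Table 1 lists the HARS, Timeline Follow-Back and urine drug screen together as primary outcomes, and Section VI models opioid use and the HARS separately. That wording adds no weight here.

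**Conclusion.** The point holds as a wording defect of modest consequence. The plan's only stated label for Stage 2 can be met by equal improvement in both arms, and so does not answer the question in Aim 2. This follows from the text and needs no numerical assumption. Aim 2 inference, the sample size and the between-arm estimate are unaffected.

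A reader might infer that Stage 2 would be sized on a within-arm effect. The documents do not say so, and the surrounding paragraph points the other way. The precision figures rest on 1:1 allocation, baseline adjustment and the plan's own correlations; they describe the cost of the remedy and are not evidence for the defect.

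**What to change.** Replace the parenthesis in Section VI with: *(i.e., improvement in ICBT relative to IDC at week 12 on HARS and on opioid use, judged from the mixed-model ICBT minus IDC effect with its 95% CI)*. Then add:

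- As a supportive analysis, the ICBT minus IDC difference in the proportion with clinically significant change on the HARS, with its 95% CI. State the cut-off and how patients without a week 12 score are classified.
- A statement that within-arm change is descriptive only.

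No pass/fail margin is needed.

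The cost is a few sentences, using models already planned, plus one small supportive analysis with its own missing-data rule. No new data or change in sample size is required. The drawback is imprecision: an interval of roughly half an SD either side on the HARS will often leave the judgement open, and the report should say so.
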